2.4.5.2 Analysis of Laboratory Variables

Clinical laboratory variables that will be analyzed include hematology tests, serum chemistry tests and coagulation tests (see Section 2.1.4.2 for the complete list of parameters).

Laboratory data for hematology and serum chemistry tests will be reported in summary tables and listings. Laboratory data for coagulation and serology tests will be presented in listings. Individual values outside the laboratory reference ranges will be identified (by “H” for high and “L” for low) in the data listings displaying the absolute values for each subject.

Continuous laboratory test results will be summarized descriptively by cohort for actual values and for changes from baseline. Number and percentage of subjects with laboratory abnormalities (H/L) will be presented. Visits to be summarized include all scheduled post-baseline visits.

Shift table from baseline to the worst post-baseline tests will be presented based on laboratory abnormalities (H/L). Laboratory tests that have high and low abnormalities will be summarized separately for each direction (e.g., hypocalcemia and hypercalcemia).

Drug-Induced Liver Injury (DILI)

The liver function tests, namely AST, ALT, total bilirubin (TBL), and alkaline phosphatase are used to assess possible drug induced liver injury. Evaluations of drug-induced serious hepatotoxicity (eDISH) plot (Hy's Law graphs) of distribution of peak values of ALT, AST and the maximum of ALT and AST versus peak values of total bilirubin will also be presented. Similarly, a graph for ALT vs. TBL and a graph for AST vs. TBL will be provided.

[2.4.5.3 Analyses of Vital Sign Variables](#)

Summary tables of vital signs and change from baseline will be presented for all scheduled visits where vital signs were assessed. All recorded vital sign data will be listed.

[2.4.5.4 Analysis of Physical Examination Variables](#)

Physical examination data will be presented in a data listing.

[2.4.5.5 Analysis of Electrocardiogram Variables](#)

ECG interpretation will be tabulated as frequencies by visit and time point, and in a shift table of baseline vs. worst post-baseline observation. Results per time point and free-text specifications of abnormalities will be listed.

[2.4.6 Study Treatment Exposure and Compliance](#)

Treatment exposure and compliance variables will be summarized as quantitative variables (N, mean, SD, median, Q1, Q3, minimum, and maximum). The percentage of subjects who have a compliance of <80%, 80% to <100%, and >=100% will be tabulated by cohort.

[2.4.7 Analyses of Pharmacokinetics](#)

Pharmacokinetics for ublituximab

An independent SAP will be issued to detail the conduct of population PK and exposure-response analyses.

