### 10.7.2 ABNORMAL LABORATORY VALUES AND VITAL SIGNS

---

The reporting of abnormalities of vital signs as adverse events should be avoided. Abnormalities of vital signs should not be reported unless any criterion for an SAE is fulfilled, the vital signs abnormalities cause the patient to discontinue trial treatment, or the investigator insists that the abnormality should be reported as an AE. Abnormal laboratory results should be noted in the eCRF as an adverse event if they are associated with an overdose, require or prolong inpatient hospitalization, or are otherwise considered clinically significant by the investigator. If an abnormal laboratory value or vital sign is associated with clinical signs and/or symptoms, the sign or symptom should be reported as an AE, and the associated laboratory value or vital sign should be considered additional information that must be collected in the relevant eCRF. If the laboratory abnormality is a sign of a disease or syndrome, only the diagnosis needs to be recorded on the SAE Report Form or AE eCRF.

Clinical Laboratory Results will be summarized. Summary statistics for actual values and for changes from baseline will be tabulated for laboratory results by scheduled visit. Subjects with laboratory values outside of the normal reference range at any post-baseline assessment will be summarized, and graded per NCI CTCAE Version 4.0 when applicable. Patient incidence of laboratory toxicity will be summarized by treatment group and maximum grade for each laboratory test.

---

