2.4.9 Analyses of Immunoglobulins

The descriptive summary and change from baseline of Immunoglobulins will be summarized by cohort. A listing will be provided for Immunoglobulins data.

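### SAP 2.4.5.2 counts laboratory abnormalities by High/Low only and omits the maximum-CTCAE-grade table promised in Protocol 10.7.2; fibrinogen is left in listings

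*SAP*

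**What the plan says.** Protocol 10.7.2 sets out three laboratory outputs. The first is descriptive: "Summary statistics for actual values and for changes from baseline will be tabulated for laboratory results by scheduled visit". The second concerns abnormal values: "Subjects with laboratory values outside of the normal reference range at any post-baseline assessment will be summarized", with CTCAE v4.0 grading added where it applies. The third is the graded table: "Patient incidence of laboratory toxicity will be summarized by treatment group and maximum grade for each laboratory test".

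SAP 2.4.5.2 plans descriptive summaries of values and changes from baseline by cohort, and then "Number and percentage of subjects with laboratory abnormalities (H/L) will be presented". It adds a shift table from baseline to the worst later result, also on High/Low, and eDISH plots for the liver tests. For coagulation, "Laboratory data for coagulation and serology tests will be presented in listings". SAP 2.1.4.2 defines coagulation as PT/INR and fibrinogen.

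Immunoglobulins are handled separately in SAP 2.4.9: "The descriptive summary and change from baseline of Immunoglobulins will be summarized by cohort", plus a listing.

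**The concern.** The protocol's third output has no counterpart in the SAP. CTCAE is not mentioned in the SAP text, and no reason is given for leaving grading out. In the High/Low tables a slightly low neutrophil count and a life-threatening one are the same entry.

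This matters because the trial is meant to choose a dose and infusion time, and several of its safety rules use grade. Protocol 5.1.1 defines hematologic DLTs by grade, and the dose-modification guidance in 6.2.1.1 turns on Grade 3 or 4.

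There is also a point about traceability. Protocol 9 makes the SAP the place for details of data presentation and has the study report describe deviations from the SAP. A report without the graded table would comply with the SAP, so the omission need not be reported as a deviation.

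**Working it through.** No design figure such as power or alpha is involved. The check is a comparison of texts plus a count of tests.

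**1. Count of tests (SAP 2.1.4.2 and 2.4.9, Protocol 7.1.1).** Hematology 11 + chemistry 18 = 29. Adding fibrinogen (1) and IgG, IgM and IgA (3) gives 29 + 1 + 3 = 33 tests with post-baseline samples. PT/INR is left out because it is drawn on Day 1 only.

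**2. Protocol 10.7.2 against the SAP.**

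| Protocol output | SAP |
|---|---|
| Values and changes by visit | Planned for the 29 tests and for the immunoglobulins; not for fibrinogen |
| Out-of-range summary | Planned for 29 of 33; 33 - 29 = 4 without one (fibrinogen, IgG, IgM, IgA) |
| CTCAE grading, incidence by maximum grade | Not planned for any test |

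The protocol's own DLT and dose-modification text names at least five tests by grade: neutrophils, platelets, hemoglobin, ALT and AST. The SAP has a maximum-grade table for 0 of these 5.

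**3. What the High/Low tables can show.** Take a cohort of 8, assuming the two placebo subjects who cross over are counted with their cohort. One subject is 1/8 = 12.5%. If k subjects are flagged Low, the High/Low table alone is compatible with 0 to k subjects at Grade 3 or 4, that is 0% to k x 12.5%. For k = 2 this is 0% to 25%. The value of k is only an illustration.

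The shift table adds little for neutrophils and platelets. Both must be normal at entry (Protocol 3.2, item 12) and before each infusion (Protocol 5.2). There is therefore one baseline row, and every fall goes from Normal to Low.

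**4. What the other SAP outputs add.**

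- *Minima and maxima.* The general convention in Protocol 9.2 includes them. A cohort minimum can show that the number of severe values is zero or at least one, but not how many. In the k = 2 example, a severe minimum leaves one or two. By-visit summaries also use only the result nearest the target day in each window, and the others are listed (SAP 2.1.4.2), so a low point at an unscheduled draw can be missed.
- *Worst values.* SAP 2.4.5 allows summaries of the value and/or the worst value, for measurements based on central laboratory or reading. It mentions no grade.
- *Grade 3+ adverse events.* Protocol 10.7.2 has a laboratory result recorded as an adverse event for overdose or hospitalization, "or are otherwise considered clinically significant by the investigator". The table therefore depends largely on reporting decisions.
- *Maximal-severity adverse event table.* It uses mild, moderate and severe (SAP 2.4.5.1).
- *DLT tables.* They hold events collected as DLTs; Protocol 5.1.1 ties these to the first 4 weeks of treatment.
- *eDISH plots.* Liver tests only.
- *Listings.* Values carry H or L flags, and the reader would have to grade them.

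None of these gives a count of subjects by laboratory grade.

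**5. Fibrinogen.** Protocol 7.1.1 puts it on the hematology schedule, so repeated post-baseline values exist and can be tabulated.

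**The case against.** The strongest reply is that most of Protocol 10.7.2 is carried over: continuous summaries and out-of-range counts for 29 tests, and descriptive summaries for immunoglobulins. In cohorts of about eight, minima and listings will show a severe fall to anyone who looks. DLTs have their own eCRF collection, table and listing, and a maximum-grade table could not identify a DLT that requires a duration of more than 7 days. Safety analysis is descriptive, and Protocol 10.7.2 still stands, so the sponsor can produce the table anyway. All of this is correct. It narrows the gap to the graded output and fibrinogen, but it does not supply the subject count by grade.

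A reader might infer that the protocol acts on grade rather than on High/Low, and that Grade 1 or 2 never leads to a hold. The documents do not support this. Protocol 5.2 requires normal neutrophils and platelets before infusion, and it holds dosing for ALT or AST above 5 times the upper limit. The graded holds in 6.2.1.1 are recommendations under investigator discretion.

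A reader might also try to estimate how many severe cases would be hidden, since Protocol 8.1.1.1 lists neutropenia and thrombocytopenia as common (>20%). That list gives no grade and does not show what the rate would be in MS, so it cannot provide such an estimate.

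**Conclusion.** The point holds as a protocol-to-SAP mismatch and should be corrected. The graded incidence table in Protocol 10.7.2 is absent for every test, including all five that the protocol names by grade. Fibrinogen has no summary table although it is sampled repeatedly. The missing out-of-range counts for IgG, IgM and IgA are minor.

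The documents do not support saying that the SAP abandons the protocol's laboratory plan, or that severe abnormalities would go unseen. The loss is a count of subjects by laboratory grade and cohort.

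The protocol requires grading only when applicable, and the documents do not say which tests have a CTCAE grade, so the number of missing graded rows cannot be stated. For immunoglobulins the point rests on the out-of-range commitment, not on grading. Primary efficacy is unaffected.

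**What to change.** In SAP 2.4.5.2, add by cohort and total the n (%) of subjects by maximum post-baseline CTCAE v4.0 grade for each gradable test, with a shift from baseline grade to worst grade. List the gradable tests. Move fibrinogen into the summary and High/Low tables; PT/INR can stay in listings.

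If the sponsor means to drop the graded table, the SAP should say that this departs from Protocol 10.7.2 and give the reason.

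Optionally, in SAP 2.4.9 add n (%) below the lower limit for IgG, IgM and IgA. This depends on local reference ranges being in the database. Protocol 14.2 requires copies of the ranges to be provided, but the documents do not confirm that they are captured as data.

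The cost is SAP wording and a few tables. For hematology and chemistry, the values and ranges already needed for the High/Low flags should largely suffice, and the flagged listings already call for fibrinogen ranges.

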### 5.1.1 DOSE-LIMITING TOXICITY

---

Toxicity will be assessed utilizing the National Cancer Institute Common Terminology Criteria for Adverse Events (NCI CTCAE) v4.0 (<http://evs.nci.nih.gov/ftp1/CTCAE/CTCAE>).

Toxicity will be considered dose-limiting if it occurs during the first 4 weeks of treatment and is considered at least possibly related to ublituximab. Any event defined below, unless the investigator considers the event clearly unrelated to study drug or due to extraneous causes, will be considered a dose-limiting toxicity.

Dose-limiting toxicities will be defined as the following:

- Grade 4 anemia; Grade 4 neutropenia or thrombocytopenia lasting >7 days; Grade  $\geq 3$  febrile neutropenia; and Grade  $\geq 3$  thrombocytopenia with Grade >2 hemorrhage;
- Grade  $\geq 3$  non-hematologic toxicity unresponsive to standard supportive care measure with the exception of:
  - Grade  $\geq 3$  ALT/AST elevation that resolves to  $\leq$  Grade 2 within 7 days;
  - Infusion related reactions (IRR's) Grade  $\geq 3$  related to ublituximab occurring at the 1st infusion, which does not affect continuation to subsequent infusions
- Treatment delay of  $\geq 14$  days due to unresolved toxicity; and
- Non-hematologic toxicity of Grade 2 (at any time during treatment) that, in the judgment of the Investigators, Study Chair, and the Medical Monitor, is dose-limiting.

Adverse events meeting the above definitions but are clearly unrelated to study drug will not be considered DLTs. In rare instances an event may fall within the definition of a DLT as defined above but the event may not be considered a DLT (i.e., not clinically meaningful/significant). If this occurs, a meeting with the Investigator(s), the Medical Monitor, and the Study Chairs, will take place to thoroughly review the event and supporting data, and the reasons for not considering the event a DLT will be clearly documented with supporting rationale. In addition, other events may occur which do not meet the definition of a DLT but are concerning to the Investigator(s), Medical Monitor, and Study Chairs, and may be then considered to be DLTs.

---

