### 10.5 ADVERSE EVENTS (AE'S) AND TREATMENT EMERGENT ADVERSE EVENTS (TEAE'S)

---

All AEs and SAEs occurring on study will be listed by patient. The frequency and percentages of subjects with treatment-emergent adverse events (TEAEs) will be tabulated by system organ class (SOC) and PT, where treatment-emergent is defined as any AE that:

- Occurs after first dosing of study medication and through the end of the study or up through 30 days after the last dose of study treatment, or

- Is considered treatment-related regardless of the start date of the event, or
- Is present before first dosing of study medication but worsens in intensity or the investigator subsequently considers treatment-related.

TEAEs that are considered at least possibly related to study treatment will be tabulated as well as deaths, SAEs, and events resulting in treatment discontinuation.

AEs that occur after informed consent but before first dosing of study medication will not be summarized but will be listed.

At each level of summarization, a patient will be counted only once for each AE, SOC, or PT experienced within that level. In the summation for AE severity, within each level of AE, SOC, or PT experienced, the one with the highest severity will be included. In the summation for AE's relationship to the study drug, within each level of AE, SOC, or PT experienced, the one with the closest relationship to the study drug will be included.

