## 10.6 DEFINITIONS OF ADVERSE EVENTS

---

An adverse event (AE) is any untoward medical occurrence in a patient or clinical investigation patient administered a pharmaceutical product. An AE does not necessarily have to have a causal relationship with this treatment. An adverse event (AE) can therefore be any unfavorable and unintended sign (including an abnormal laboratory finding, for example), symptom, or disease temporarily associated with the use of a medicinal product, whether or not considered related to the medicinal product. This includes any occurrence that is new in onset or aggravated in severity or frequency from the baseline condition.

In clinical studies, an AE can include an undesirable medical condition occurring at any time, including run-in or washout periods, even if no trial treatment has been administered. The NCI Common Terminology Criteria for Adverse Events (CTCAE) v4.0 is to be used for the grading of severity of symptoms and abnormal findings. For adverse events not covered by the NCI-CTCAE Version 4.0 grading system, the following definitions will be used:

- **Grade 1:** Mild; asymptomatic or mild symptoms; clinical or diagnostic observations only; intervention not indicated.
- **Grade 2:** Moderate; minimal, local or non-invasive intervention indicated.
- **Grade 3:** Severe or medically significant but not immediately life-threatening; hospitalization or prolongation of hospitalization indicated.
- **Grade 4:** Life-threatening consequences; urgent intervention indicated.
- **Grade 5:** Death related to AE.

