2.4.5.1 Analysis of Adverse Events

The Treatment-Emergent Adverse Events (TEAE) is defined as any AE that:

- Occurs after first dosing of study medication and through the end of the study or up through 30 days after the last dose of study treatment, or
- Is considered treatment-related regardless of the start date of the event, or
- Is present before first dosing of study medication but worsens in intensity or the investigator subsequently considers treatment related.

Dose-limiting toxicity (DLT) is defined in protocol section 5.1.1 and collected in eCRF.

Adverse event incidence tables will be presented by cohort and total, the number (n) and percentage (%) of subjects experiencing an AE. In a subset of tables, also all occurrences will be counted providing a severity of occurrence of the AE. The denominator for computation of percentages is the Safety Population within each cohort.

Not treatment emergent AE(s) summary:

- Listing of (not treatment emergent) AEs showing cohort, subject identifier, SOC, PT, verbatim term, date and day of onset, end date/time, duration, outcome, severity, date of death (if relevant), relationship to study treatment, action taken, AE seriousness and criteria.

TEAE(s) summaries:

The following TEAE summaries will be generated for the Safety Population.

Overview of TEAEs, summarizing number (%) of subjects with any

- (related/all) TEAE
- (related/all) Serious TEAE
- DLT
- (related/all) TEAE leading to death
- (related/all) TEAE of grade 3 or higher
- (related/all) TEAE leading to drug interruption
- (related/all) TEAE of special interest (AESI)
- (related/all) TEAE leading to permanent discontinuation

- TEAEs by primary SOC and PT, showing number (%) of subjects with at least one TEAE, sorted alphabetically by SOC and decreasing incidence of PTs within SOC for the total column. This sorting order will be applied to all other tables, unless otherwise specified.
- TEAEs by PT, sorted by decreasing frequency in the total column.
- All at least possibly drug related TEAEs by primary SOC and PT, showing number (%) of subjects with at least one possibly related TEAE, sorted by sorting order defined above.
- All TEAEs by maximal severity, presented by primary SOC and PT, showing number (%) of subjects with at least one TEAE by severity (ie, mild, moderate, or severe), sorted by sorting order defined above.

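### SAP 2.4.5.2 replaces the laboratory summary by maximum CTCAE grade promised in protocol 10.7.2 with high/low flags, so its laboratory count and shift tables treat Grade 1 and Grade 4 cytopenias alike

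*SAP*

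**What the plan says.** **Laboratory data, protocol.** Section 10.7.2 says that subjects with out-of-range post-baseline values "will be summarized, and graded per NCI CTCAE Version 4.0 when applicable". It then specifies the table: "Patient incidence of laboratory toxicity will be summarized by treatment group and maximum grade for each laboratory test".

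**Laboratory data, SAP.** Section 2.4.5.2 plans descriptive statistics of values and changes by cohort, and listings of each subject's values. For counts of subjects it says "Number and percentage of subjects with laboratory abnormalities (H/L) will be presented". For shifts it says "Shift table from baseline to the worst post-baseline tests will be presented based on laboratory abnormalities (H/L". Coagulation results are listed only. The section has no graded laboratory table and does not mention CTCAE.

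**Adverse events, protocol.** Section 10.6 states: "The NCI Common Terminology Criteria for Adverse Events (CTCAE) v4.0 is to be used for the grading of severity of symptoms and abnormal findings". It also defines Grades 1 to 5 for events that CTCAE does not cover. Under section 10.5, when a patient has several occurrences, "the one with the highest severity will be included".

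**Adverse events, SAP.** Section 2.4.5.1 keeps a maximal-severity table by system organ class (SOC) and preferred term (PT), presented "by severity (ie, mild, moderate, or severe". It also plans an overview row for treatment-emergent events of Grade 3 or higher, DLT tables, serious events by seriousness criterion, and deaths.

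**The concern.** Choosing a dose and infusion time is a primary objective, so the comparison of safety between cohorts has to carry weight. Several of the protocol's safety rules are written in CTCAE grades. The DLT definition in section 5.1.1 includes "Grade 4 neutropenia or thrombocytopenia lasting" more than 7 days, and the laboratory dose-modification tables in section 6.2.1.1 turn on Grade 3 or 4. Section 8.1.1.1 lists neutropenia and thrombocytopenia among the common (>20%) related events seen with single-agent ublituximab.

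A table that records only low or not low cannot show whether a cohort's cytopenias were trivial or life-threatening. The final report would then lack the one laboratory table that the protocol specifies for this purpose.

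**Working it through.** The plan states no figure to reproduce. The check sets the two documents side by side, then counts what a flag table can and cannot distinguish.

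**1. What each document tabulates**

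| Output | Protocol 10.7.2 | SAP 2.4.5.2 |
|---|---|---|
| Incidence for each test | By maximum CTCAE grade | High/low flag only |
| Shift table | None specified | High/low flag only |
| Values and changes | Descriptive, by visit | Descriptive, by cohort; listings |

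The graded incidence table is the item that has disappeared.

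**2. Why the shift table adds little for neutrophils and platelets**

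Exclusion criterion 12 removes subjects with either count out of range, and protocol 5.2 requires both in range before infusion. SAP 2.1 sets baseline at the last value on or before the first ublituximab dose. Nearly every later neutropenia or thrombocytopenia is therefore the same normal-to-low shift, and the shift table largely repeats the flag count.

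**3. What the flag hides**

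Take one test in one direction, with each subject's maximum laboratory grade from 0 to 4. Grade 5 is death and is not a laboratory value. Protocol 10.7.2 applies grades to out-of-range values, so I assume that every graded low value is flagged low.

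- Possible grade distributions among n subjects: C(n+4, 4). For n = 6, C(10, 4) = 210.
- Possible flag counts: n + 1 = 7.
- Patterns behind a count of k flagged subjects, each Grade 1 to 4: C(k+3, 3). For k = 2, C(5, 3) = 10, all printed as 2/6 (33.3%). For k = 3, C(6, 3) = 20, all printed as 3/6 (50.0%).
- Check: 1 + 4 + 10 + 20 + 35 + 56 + 84 = 210.

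If the two placebo subjects who cross over are counted with their cohort, n = 8. There are then 495 distributions and 9 flag counts. The 10 and 20 patterns do not change, because they depend only on k. These are counts of possibilities, not probabilities.

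**4. Whether other planned outputs recover the grade**

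- *AE tables.* Under protocol 10.7.2 and 10.11.2, a laboratory value is recorded as an AE if it is linked to overdose or hospitalisation, or if the investigator judges it clinically important. Grade alone does not trigger recording.
- *DLT tables.* The DLT window is the first 4 weeks of treatment. It covers the Day 1 and Day 15 infusions but not the week 24 infusion. Stand-alone Grade 4 neutropenia or thrombocytopenia must also last more than 7 days.
- *Overview row for Grade 3 or higher.* It is not split by SOC or PT, so it does not isolate cytopenias, and it depends on AE recording.
- *Value summaries.* Under SAP 2.1.4.2, when several results fall in one window, the by-visit summary uses the one nearest the target date and the rest are only listed. An off-target nadir can drop out. SAP 2.4.5 leaves open whether the worst value is summarised, and a minimum does not count subjects by grade.
- *Listings.* They contain everything but are not an incidence summary. The peak-value plots cover liver tests only.

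**5. AE severity table**

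In protocol 10.6 Grade 1 is mild, Grade 2 moderate, Grade 3 severe, Grade 4 life-threatening and Grade 5 death. The SAP's three labels stop at severe. Grades 4 and 5 are either folded into severe or left without a category; the SAP does not say which. The split among Grades 3, 4 and 5 by SOC and PT is lost in that table.

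**The case against.** The strongest reply is that this is a matter of reporting alignment in a descriptive, unpowered study. Cohort progression rests on safety review by the monitoring board during the trial, not on the final tables. Values are summarised and listed, and grades can be derived later. Protocol 10.4 itself lists short Grade 4 neutropenia and thrombocytopenia as AEs, exempt only from expedited reporting, so the protocol expects some of them in the AE data. All of this stands. It limits the consequence but does not supply the promised table.

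A reader might also infer more than the documents support:

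- *That AE tables also count Grade 1 and Grade 4 alike.* They do not. Grade 1 is mild, and only the Grade 4 event can enter the row for Grade 3 or higher.
- *That the protocol promised AEs by maximum CTCAE grade in those words.* Section 10.5 speaks of highest severity. Maximum grade is specified only for laboratory tests.
- *That Grade 4 and 5 events are invisible.* Fatal events have their own SOC and PT table. Serious events are tabulated by seriousness criterion, which includes death and immediate threat to life. DLTs are tabulated and listed.
- *That all dosing holds are defined by grade.* Protocol 5.2 uses the normal range for neutrophils and platelets and a multiple of the upper limit of normal for ALT/AST, while 6.2.1.1 uses grades. Those passages need reconciling in their own right and do not carry this point.
- *That the >20% frequency applies to multiple sclerosis.* Section 8.1.1 does not state the population, and the completed phase I work described was in leukaemia and lymphoma.

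**Conclusion.** The point holds for the laboratory tables. SAP 2.4.5.2 departs from a specific commitment in protocol 10.7.2 without explanation, and its count and shift tables cannot separate a Grade 1 from a Grade 4 cytopenia. For 3 of 6 subjects flagged low, 20 grade patterns collapse into one entry. Magnitude survives in value summaries and listings, and AE and DLT tables recover laboratory grade only partly. It would go too far to say that severity information is lost or cannot be recovered.

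The AE severity table is a secondary point: it collapses or omits the distinction among Grades 3, 4 and 5, with partial cover from other planned outputs.

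The consequence is a weaker safety comparison between cohorts in a trial meant to choose dose and infusion time. No test, estimate or stopping boundary changes. The conclusion assumes that no separate output specification restores the graded table; none appears in the documents supplied. It is worth correcting in the SAP, at moderate priority.

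**What to change.** In SAP 2.4.5.2, add subject incidence by maximum post-baseline CTCAE v4.0 grade for each gradable laboratory test, by cohort and by direction where both apply. Use all scheduled and unscheduled values rather than the one nearest the target day. This meets protocol 10.7.2. Include any gradable coagulation test, since the SAP now sends coagulation to listings alone. Keep high/low flags for tests without a grade.

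Preferably base the shift table on grade as well, from baseline to worst post-baseline. That is an improvement, not a protocol commitment.

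In SAP 2.4.5.1, replace the three severity labels with maximum CTCAE Grade 1 to 5 by SOC and PT.

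If the sponsor prefers to keep the flags, the SAP should record and justify the departure from protocol 10.7.2.

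The cost is some SAP wording, a grading derivation and a few extra tables. The data are already collected, and no visit, sample or sample size changes.
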